### I. Hypotheses and Specific Aims:

NAFLD has become a major public health problem in the United States because of its high prevalence, association with serious cardiometabolic complications and progression to cirrhosis and liver failure. NALFD is characterized by increased intrahepatic triglyceride content (>5.5% of the liver volume or more than 5% of hepatocytes contain triglyceride), and progression to inflammation and fibrosis. NAFLD is associated with increased risk of developing type 2 diabetes (T2D), hypertension, and coronary heart disease. Obesity is an important risk factor for NAFLD; NAFLD occurs in ~70% of adults with obesity and in ~35% of children with obesity.

However, data from several studies suggest the histological manifestations and progression to fibrosis are different in adults and children with NAFLD. Differences between the ages suggest distinct pathology as i) Youth with NAFLD may progress to liver failure fairly rapidly, by early adolescence, as compared to a more indolent course in adults and ii) biopsy criteria are distinct with periportal steatosis and fibrosis in youth and sinusoidal ballooning and fibrosis in adults. Alterations in mitochondria function, secondary to an influx of substrates from the diet and dysfunction muscle and adipose tissue are thought to contribute to NAFLD. We hypothesize that alterations in mitochondrial energy and substrate metabolism are involved in the pathogenesis and pathophysiology of NAFLD and these factors differ in children and adults. A better understanding of intrahepatic regulation of energy and intermediary metabolism in children and adults with NAFLD is needed to provide a framework for future studies designed to prevent and treat NAFLD across the lifespan.

Nonalcoholic fatty liver disease (NAFLD), characterized by an increase in intrahepatic triglyceride (IHTG) content (i.e. steatosis) with or without inflammation and fibrosis (i.e. steatohepatitis), is a common complication of obesity. It is estimated that 70% of adults and 35% of children with simple obesity have NAFLD, with rates of 50% in polycystic ovarian disease and even higher in diabetes. In particular, youth with severe obesity who are candidates for bariatric surgery have even high rates of NAFLD, in excess of 50%. Further it is not clear if bariatric surgery decreases the risk of progression of NAFLD, as the influx of free fatty acids during rapid weight loss may actually lead to worsening of NAFLD, if the liver cannot metabolize these increased substrates.

Data from a series of studies conducted in animal models and in people suggest hepatic mitochondrial metabolism is directly involved in the pathogenesis and pathophysiology of NAFLD. Animal and human studies have demonstrated that both the anaplerotic and cataplerotic cycles of hepatic mitochondria are upregulated in NAFLD. Excess carbon from

surplus calories (glucose or free fatty acids (FFA)) are directed to the TCA cycle in the mitochondria, but the TCA cycle cannot serve as a carbon sink, and thus cataplerosis is also increased, providing substrates for fatty acid esterification (FAE) and *de novo* lipogenesis. In addition, increased TCA cycle activity increases the production of reactive oxygen species (ROS), which cause inflammation and subsequent fibrosis (Fig. 1). Pediatric and adult NAFLD are not the same; hepatic steatosis is located primarily in the periportal areas of the liver in youth but in perisinusoidal areas in adults, and youth typically have more rapid progression to fibrosis. The mechanism(s) responsible for these differences is not known, but could be related to differences in mitochondrial dysfunction. Together, these studies underscore the need for sophisticated metabolic studies in both children and adults to better understand the factors involved in the pathogenesis and pathophysiology of NAFLD.

Methods used to assess hepatic mitochondrial energy metabolism include: i) obtaining liver tissue and assessing *ex vivo* mitochondrial ATP production and ii) phosphorus magnetic resonance spectroscopy (P-MRS) to measure phosphate concentrations. The existing P-MRS procedure is limited because it assesses non-dynamic concentrations of P metabolites or the response to a specific dietary challenge, but does not provide a direct measure of global hepatic mitochondrial energy metabolism. In addition, this procedure requires excessive participant time in the magnet which is burdensome, particularly for children, and expensive. *Therefore, there is an unmet need for a non-invasive research method that can assess global dynamic hepatic mitochondrial energy metabolism.*

New methods that magnetically remove the  $\gamma$ -phosphate of ATP via inversion transferase sequences allow for dynamic measurement of phosphate kinetics. This methodology has been successfully used to assess ATP production *in vivo* in skeletal muscle tissue, but has not yet been applied to the liver. This cross-institution project will allow the development of a non-invasive *in vivo* methods to study hepatic energy metabolism. *We will combine the novel P-MRS method with concomitant *ex vivo* analysis of mitochondrial functional capacity by using the Orobos analysis of liver tissue obtained during bariatric surgery to provide a unique and comprehensive analysis of hepatic energy and substrate metabolism in human participants across the lifespan. Metabolic status will also be categorized at that time. A follow-up study in individuals a year later will allow for evaluation of the long-term effects of bariatric surgery on NAFLD risk and progression and or regression in this youth population.*

In the wake of our national obesity epidemic, bariatric surgery has become a critical option for many youth with severe obesity for management of obesity and related complications such as risk for type 2 diabetes and NAFLD. Bariatric surgery is very effective in inducing weight loss, although the effects on NAFLD are unclear, and may vary by time post-operatively. Following bariatric surgery, there is adipose tissue breakdown in the negative energy state, with very large influxes of free fatty acids to the liver. These FFA can be oxidized in the mitochondria for ATP generation, or stored in the liver. Especially in individuals who have underlying mitochondrial defects in the liver, as is known to occur in NAFLD, this can lead to excess deposition of FFA in the liver, and potential worsening on NAFLD state prior to resolution. One limited study in 20 youth with repeat biopsies showed 100 percent improvement in glucose and NAFLD markers and 90% improvement in fibrosis, although full assessment of diabetes risk was not performed. NAFLD status is the best predictor for development of type 2 diabetes in youth and thus it is important to assess the 2 components of diabetes risk- insulin resistance and insulin secretion. Predictors for improvement of NAFLD beyond weight loss are not clear, especially in youth. A better understanding of the post-prandial nutrient handling following bariatric surgery is needed to further optimize post-surgery therapies to improve NAFLD.

## **HYPOTHESIS:**

- 1) NAFLD status will be improved by 1-year post-bariatric surgery and this may relate to post-prandial glucose and FFA concentrations and hepatic mitochondrial metabolism.

- 2)  $^{31}\text{P}$ -MRS, blood and liver isotopomer analysis and metabolomics can be used as surrogate measures to assess hepatic function in NAFLD

**Aim 3:** Determine hepatic mitochondrial activity in vivo using  $^{31}\text{P}$ -MRS, isotopomer and plasma metabolomic analysis and ex vivo using Orobos in youth with severe obesity. NAFLD features will be further characterized using liver histology to assess steatosis and NASH and by using MR elastography to assess global hepatic fibrosis. Alterations in glucose and fat metabolism will be assessed with a mixed meal tolerance test (MMT). Comparisons between these surrogate markers and biopsy samples will help identify minimally invasive measures to predict NAFLD severity without the need for future biopsies.

**Hypothesis:** We hypothesize that alterations in mitochondrial energy and substrate metabolism are involved in the pathogenesis and pathophysiology of NAFLD. A better understanding of intrahepatic regulation of energy and intermediary metabolism in children with NAFLD is needed to provide a framework and identify minimally invasive biomarkers for future studies designed to prevent and treat NAFLD.

**Rationale:** NAFLD is unfortunately an increasing common complication of pediatric obesity. Youth onset metabolic disease confers an early and more severe morbidity and earlier mortality than adult onset disease, emphasizing the urgency of treating this population.

**Methods:** We will compare multiple methods of non-invasive and minimally invasive measure of hepatic metabolism with the gold standard but invasive liver biopsy.  $^{31}\text{P}$ -MRS and isotopomer analysis will be used to assess hepatic oxidative phosphorylation, MRI for hepatic fat fraction

and MR elastography for liver stiffness. Serum for metabolomics analysis will be collected and metabolites which related to MR and biopsy measure identified (targeted analysis for fatty acids, acycarnitines and bile acids). Ex vivo measures of mitochondrial function will be measured in liver biopsy samples (already being collected during bariatric surgery for clinical NALFD staging) with oroboros technologies. NAFLD staging data from the pathology lab will also be collected. Alterations in glucose and fat metabolism will be assessed with a mixed meal tolerance test (MMT).

### III. Research Methods

#### A. Outcome Measure(s):

Primary Outcome Measure(s): Post-prandial glucose, insulin, C-peptide, GLP-1 and glucagon dynamics as assessed with an MMTT.

Secondary Outcome Measure(s): Hepatic fat content per MR, and biopsy, Stiffness per MR elastography, and fibrosis per biopsy. . Exploratory Aims: ex vivo hepatic mitochondrial activity per biopsy, isotopomer analysis and Hepatic mitochondrial activity per P-MRS. Likely contributors to above measures: Lipid/glucose markers:(fasting C-peptide and lipid panel, HbA1c); hepatic markers:(c-reactive protein, glucagon, GLP-1 and leptin, adiponectin, AST, ALT, GGT) Body size and composition: (BMI, waist/hip ratio, Bodpod, hepatic visceral fat via MRI), Whole body fat oxidation at rest as measured with a metabolic cart; Physical activity/diet:(accelerometer, activity survey (3DPAR); Food frequency survey). Questionnaires for presence of obstructive sleep apnea. Questionnaires for perceived mental strengths and difficulty (note there is no assessment of suicidality on this tool).

#### B. Description of Population to be Enrolled:

Study staff aims to enroll 16 obese boys and girls 13-20 years old.

Ethnic Categories	Gender		
	Females	Males	Total
Hispanic or Latino	7	6	13
Not Hispanic or Latino	6	6	12
Ethnic Categories: Total of All Participants	13	12	25
Racial Categories			
American Indian/Alaska Native			
Asian			
Native Hawaiian or Other Pacific Islander	2	2	
Black or African American	2	2	
White	9	8	
Racial Categories: Total of All Participants *	13	12	25

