### **Overall Project Statistical Plan:**

SA1: Changes in hepatic fat will be compared to changes in insulin resistance, beta cell function and 31P-MRS and metabolomics score. Results will be adjusted for absolute and percent weight loss.

SA3: Pearson correlations between 31P-MRS rate of ATP recovery, metabolomics outcomes, hepatic fat fraction, MRE, Oroboros outcomes and biopsy scores will be performed to see which

minimally invasive measures relate most to biopsy markers. Liver measures will also be compared to insulin sensitivity and insulin secretion from the MMT.

Overall Power analysis:

SA1: The data collected for SA3 is to be preliminary data to provide background data for future additional studies in youth.

SA2/SA3: Relation of metabolic outcomes for this type of protocol typically requires 6-8 participants, especially with such a homogenous participant group. However, as it is known that African American tend to have different hepatic fat metabolism patterns compared to Hispanics, we have allowed for 10 participants.

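### The enrolment section aims for 16 participants in its text but totals 25 in the table beneath it, and nothing in the protocol reconciles the two

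*Combined protocol and SAP*

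**What the plan says.** Section III.B (Description of Population to be Enrolled) opens with "Study staff aims to enroll 16 obese boys and girls 13-20 years old". The table that follows has two blocks, each closed by a total row: "Ethnic Categories: Total of All Participants" and "Racial Categories: Total of All Participants". Both rows read 13 females, 12 males, 25 in all.

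Section VII (Overall Project Statistical Plan) gives further numbers under its power heading. For SA2/SA3 it says "Relation of metabolic outcomes for this type of protocol typically requires 6-8 participants, especially with such a homogenous participant group". It then cites a difference in hepatic fat metabolism between African American and Hispanic youth and concludes "we have allowed for 10 participants". The SA3 analysis is "Pearson correlations between 31P-MRS rate of ATP recovery, metabolomics outcomes, hepatic fat fraction, MRE, Oroboros outcomes and biopsy scores will be performed". The SA1 analysis is "Changes in hepatic fat will be compared to changes in insulin resistance, beta cell function and 31P-MRS and metabolomics score", but the power entry labelled SA1 reads "SA1: The data collected for SA3 is to be preliminary data to provide background data for future additional studies in youth".

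Section IV (Overall Project Limitations) calls the study a pilot that is probably underpowered for associations between metabolic change and NAFLD status. It expects good completion without giving a rate, and says a future revision would enlarge the cohort if more funding is found.

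**The concern.** The enrolment number is a basic protocol parameter, and here one section gives it two values. With both in force, stopping at 16 is either complete or 9 short of plan, and reaching 25 is either as planned or 9 over the stated target. Participants may be as young as 13 and undergo research procedures, so the intended number should be unambiguous.

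The number also governs what the SA3 correlations can show. The power section does not settle the matter: it brings in a different number, 10, without saying how it relates to enrolment, and supports it with a 6-8 figure that has no stated basis.

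**Working it through.** **1. Does the table really come to 25?** Inputs are the cells in Section III.B.

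- Ethnic block: Hispanic or Latino 7 + 6 = 13; not Hispanic or Latino 6 + 6 = 12; 13 + 12 = 25.
- Racial block: females 2 + 2 + 9 = 13; males 2 + 2 + 8 = 12; 13 + 12 = 25.

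The table's own total reproduces twice, from different cells. A slip in one cell or a broken row in the PDF text would not produce that agreement. The table adds correctly; the conflict is between table and text.

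**2. Size of the gap.** 25 − 16 = 9. As a share of 25, 9/25 = 36%. As a share of 16, 9/16 = 56%.

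**3. Could dropout link the two?** If 25 were enrolled to leave 16 completers, the loss d would satisfy 25 × (1 − d) = 16, so d = 9/25 = 36%. Section IV gives no dropout rate and expects low loss on the basis of earlier studies. No other section describes 25 as screened participants or an upper limit.

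**4. The 10 under SA2/SA3.** 10 < 16 and 10 < 25, so either enrolment number meets it. It could be a minimum, the expected analysable number or a subset. The glycerol drink is marked optional in the Section III.C calendar, and Section IV speaks of the tracer in only some participants. The text does not choose among these.

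**5. The 6-8 figure.** It cannot be reproduced, because no correlation, alpha, sidedness or power is given. To show what such numbers imply, assume one unadjusted Pearson test, two-sided alpha 0.05, 80% power and bivariate normality.

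- Approximate formula (Fisher z): r = tanh[(1.960 + 0.842)/√(n − 3)]. For n = 16: tanh(2.802/√13) = 0.65. For n = 25: tanh(2.802/√22) = 0.54.
- Exact calculation: given the spread of one variable (chi with n − 1 df), the test statistic is noncentral t with n − 2 df and noncentrality ρχ/√(1 − ρ²). Average the power over chi and solve for ρ. Simulation confirmed the results.

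| n | Detectable true \|r\|, exact | Range: one-sided 80% to two-sided 90% |
|---|---|---|
| 6 | 0.89 | 0.85–0.93 |
| 8 | 0.82 | 0.77–0.87 |
| 10 | 0.76 | 0.70–0.82 |
| 16 | 0.64 | 0.58–0.70 |
| 25 | 0.53 | 0.48–0.59 |

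Power at 16 and 25 is 53% and 75% if the true r is 0.5, and 98% and over 99% if it is 0.8. How much the choice of number matters therefore depends on a correlation that the documents do not give.

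These figures are optimistic for ordinal biopsy scores. With an assumed four-level score, the underlying correlations of 0.64 (n = 16) and 0.53 (n = 25) give about 73% power if the levels are equally filled, and 61% and 63% if they split 60/25/10/5.

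**6. The SA1 line.** The SA1 analysis compares changes with changes. The SA1 power entry speaks only of data collected for SA3, so Aim 1 has no sample-size statement of its own.

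**The case against.** The case on the other side is that this is a small pilot which already discloses low power, claims no confirmatory test, and needs a one-number correction. Much of that stands, and it limits the point. The disclosure in Section IV concerns power, however; it does not say how many will be enrolled.

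Four stronger readings are tempting and are not supported:

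- *That 10, 16 and 25 are in three-way conflict.* Both totals exceed 10, and the most natural reading of the SA2/SA3 sentence is a requirement that either would meet.
- *That 6-8 is a miscalculation.* No inputs are stated, so no calculation can be shown to be wrong. The figure is unsupported; the detectable correlations above rest on assumed alpha and power.
- *That the plan overstates its power.* It states no detectable effect at all. Section IV expects low power for the change associations, wording that covers SA1 and arguably SA3. The correlations also do not concern the primary outcome, which Section III.A sets as the meal-test dynamics.
- *That one figure is left over from a revision, so the other is current.* Section IV describes a possible future enlargement. It does not show that one took place.

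The racial total carries an asterisk with no note in the available text, which might have qualified it. The ethnic total has no asterisk and is also 25.

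**Conclusion.** The enrolment target is wrong as written: 16 in the text against 25 in the table, a gap of 9 that nothing in the documents explains. This rests on addition alone, needs no statistical assumption, and should be corrected. Which number is intended cannot be determined from the documents.

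The rest is optional. The role of the 10 is unclear but not contradictory, the 6-8 statement lacks a basis, and the SA1 power entry looks like a labelling slip. The detectable correlations of about 0.64 at 16 and 0.53 at 25 illustrate what the choice means. They hold only for a single unadjusted two-sided 0.05 Pearson test with 80% power, bivariate normality and complete pairs.

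**What to change.** **To correct:** the sponsor states one enrolment number in Section III.B and makes the sentence and both table blocks agree with it. If the two figures are meant to be different things, such as enrolled and completing, the section should label them so.

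**Optional, in Section VII:**

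- Say how the 10 for SA2/SA3 relates to that number: a minimum, a subset or the expected analysable number.
- Drop the 6-8 statement and say that feasibility sets the size. Alternatively, give the precision at the chosen number with its assumptions: about 0.64 at 16 or 0.53 at 25, under the conditions above, with a plain warning that power is lower for ordinal biopsy scores. An unqualified 80% claim should not be written for those scores.
- Correct the SA1 entry so that it refers to Aim 1.

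The cost is a few sentences and possibly one table. No participants, visits or assays are added by making the documents agree.

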#### Inclusion Criteria:

1. Obese youth (>95th percentile for age and sex) ages 13-20 years, scheduled for bariatric surgery
2. BMI 35-60 kg/m^2
3. Largest body circumference <200cm (in order to fit into MRI machine)

#### Exclusion Criteria:

1. Use of medications known to affect insulin sensitivity or hepatic outcomes: oral glucocorticoids within 10 days, atypical antipsychotics,

immunosuppressant agents, HIV medications, PPAR-γ or PPAR-α, metformin.

2. Infectious hepatitis
3. Alcohol abuse, (defined by the America Association for the Study of Liver Diseases as >21 drinks/week for males >14 drinks/week for females, with a drink considered 14 grams of alcohol)
4. Mitochondrial disease
5. Currently pregnant or breastfeeding women. Development of pregnancy during the study period will necessitate withdrawal from the study.
6. Severe illness requiring hospitalization within 60 days
7. Diabetes, defined as Hemoglobin A1C > 6.4%
8. Anemia, defined as Hemoglobin < 10 mg/dL
9. Diagnosed major psychiatric or developmental disorder limiting informed consent
10. Implanted metal devices that are not compatible with MRI

### C. Study Design and Research Methods

Study Calendar	Screening Visit	Baseline Visit: MMTT and MRI	Post-Surgery Visit: MMTT and MRI
Consenting and Eligibility Assessment	X		
History & Physical		X	X
Urine Pregnancy Test (females only)		X	X
Questionnaires- SEARCH Food frequency, Activity 3DPAR, Strengths and Difficulties and Sleep assessments		X	X
Bodpod		X	X
Mixed Meal Tolerance Test (MMTT)		X	X
MRI of abdomen and liver		X	X
 P-MRS of Liver		X	X
Metabolic Cart		X	X
Glycerol drink - optional		X*	X
Total Time of visit (approximately)	30 minutes	6-8 Hours	6-8 Hours
Location of Visit	CHCO CTRC Outpatient	CHCO CTRC Outpatient, and Brain Imaging Center	CHCO CTRC Outpatient, and Brain Imaging Center

The study consists of 3 outpatient visits. The Baseline Visit would be completed within two months prior to bariatric surgery, and the Post-surgery visit will be scheduled approximately 1-year post-surgery.

\*The glycerol drink will be taken the day of the Baseline visit, and in the morning of operation, then 1 year later

**NOTE:** Depending on scheduling and availability, the MRI scans can be completed on a separate visit within 10 days of the MMTT.

[figure not shown]
### SCREENING VISIT

Pediatric CTRC Outpatient Unit: Chart review of bariatric patients will be conducted for inclusion/exclusion criteria evaluation. Participants whom appear to meet eligibility criteria would then be approached about a screening visit. During this visit, patients will review and complete consent documents, have demographics and medical history confirmed, assess allergies and further evaluation of inclusion/exclusion criteria, and have anthropometrics completed for eligibility assessment.

## BASELINE VISIT 2 (FIGURE 2: MMT AND MRI)

### Overall Plan:

Figure 2: Baseline Visit

### MRI at UCD Research (Brain Imaging Center):

1. The imaging will be of the liver. Participants will undergo a standard MRI of the mid-abdomen to assess the amount of subcutaneous fat, visceral fat and percent liver fat. MR elastography will be performed to assess liver stiffness. Finally, P spectroscopy to measure concentrations of phosphate molecules including PDE, PME and PCr.

#### Abdominal/Hepatic Imaging and Elastography

Imaging will be performed on a Siemens 3 Tesla MRI magnet. Hepatic fat fraction will be performed using modification of the Dixon method as in our previous studies. Visceral adiposity will be measured using the gold standard of an MRI slice at L4-L5. Hepatic fibrosis will be measured with a standard clinical elastography sequence.

